Post-Stroke Aphasia and RTMS Treatment (PART)

Study Protocol & Statistical Analysis Plan

NCT01512264

April 1, 2019

[name], PHD, Principal Investigator

University of Alabama at Birmingham

Birmingham, AL 35294

**POST-STROKE APHASIA AND RTMS TREATMENT (PART) STUDY
NIH R01 HD068488**

PI: [name], PHD

Co-I'S:

UC: [name], PHD

**UAB: [name], PHD (BLINDED TO TREATMENT
ASSIGNMENT)
[name] (BLINDED TO TREATMENT ASSIGNMENT)**

**RTMS TREATMENT TEAM
[name]
[name], PHD
[name], PHD
[name]**

**CIAT TREATMENT TEAM
[name]
[name], SLP
[name], SLP**

OTHER STUDY PERSONNEL:

[name], BS (BLINDED TO TREATMENT ASSIGNMENT)

PART Study Protocol

This study will test two hypotheses:

Hypothesis 1: Navigated excitatory rTMS (nerTMS) will improve language outcomes when applied to the peri-stroke language areas identified by fMRI in patients with chronic (>1 year) aphasia caused by a left middle cerebral artery (LMCA) stroke when compared to sham treatment (ST); synergistic effect is expected in subjects treated with a combination of nerTMS and CIAT. Treatment response, as measured with qualitative and quantitative aphasia testing (AT), will depend on treatment duration.

Hypothesis 2: Improved language performance will be associated with increased left-lateralization of language networks following nerTMS as assessed by fMRI. This left-hemispheric shift of language processing will correlate with behavioral response to nerTMS, representing evidence of clinical efficacy; the degree of the post-intervention recovery will correlate with the degree of the left-sided language shift.

The following specific aims were designed to test these hypotheses:

Aim 1 (treatment): To determine the comparative efficacy and optimal dosing of nerTMS on aphasia recovery using a randomized, double-blind, sham-controlled study design. Subjects (15/group) will be randomly assigned to 4 treatment groups: (a) 3 weeks of nerTMS, (b) 1 week of ST+ 2 weeks of nerTMS, (c) 2 weeks of ST+1 week of nerTMS, or (d) 3 weeks of ST (control group). This design will allow systematic evaluation of the efficacy of nerTMS and its most optimal dose for language recovery. Short- and long-term outcomes will be evaluated with aphasia testing (AT) and fMRI.

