Aim 2 (imaging): To use fMRI to assess changes in language lateralization in response to nerTMS. We will examine the relationship between the degree of pre-nerTMS language lateralization (fMRI) with the post-nerTMS language outcomes (AT) and determine whether fMRI language lateralization can predict AT performance following nerTMS targeted to the left middle cerebral artery (LMCA) stroke areas.

Aim 3 (exploratory/shaping): To explore the possible synergistic effect of constraint induced aphasia therapy (CIAT) plus nerTMS on aphasia recovery in a group of 20 LMCA stroke patients. These subjects will receive 2 weeks of nerTMS enhanced by 1 hour of daily CIAT; both therapies will be administered in open-label fashion. Patients will be evaluated with fMRI and AT as above and compared to the arm "b" of the double-blind study and to CIAT data collected in an ongoing study (R01 NS048281). This aim will gather preliminary data regarding the possible synergistic effects of nerTMS and behavioral intervention.

SIGNIFICANCE

Stroke patients tend to prioritize speaking, writing and walking as the three most important rehabilitation goals. Of note is that two of these goals involve communication. This underscores the significance of developing a successful approach to aphasia treatment for the several hundred thousand new aphasia patients each year and over 1 million stroke survivors with aphasia in the U.S. alone.

Post-stroke aphasia and its impact

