
INNOVATION

The challenge for this study is to further develop and implement nerTMS as a tool for stimulating language recovery in patients with chronic post-stroke aphasia. This challenge will be addressed by conducting a randomized, sham-controlled, dose-response trial of nerTMS in order to provide class I data from a phase III treatment trial investigating fMRI-targeted treatment for chronic post-stroke aphasia (**AIM 1**). While there is evidence that nerTMS applied to the affected hemisphere may improve post-stroke motor recovery [58] and when applied to the language-dominant hemisphere in controls may promote better language skills, nerTMS has not been tested in treatment of post-stroke aphasia or in combination with other restorative therapies (CIAT; **AIM 3**). The potential impact of this study is tremendous with the potential to improve the quality of life in hundreds of thousands of Americans. We will demonstrate that nerTMS applied to the peri-stroke regions defined by fMRI promotes language recovery, and we will determine the most efficacious and the safest dose of nerTMS (**AIM 1**). Further, while the fMRI methods developed and tested by us and others are now well established, the approach of using fMRI to localize targets for nerTMS intervention and as a way of predicting the possibility of post-stroke recovery ("point of no return"; **AIM 2**) is innovative; accomplishing this aim will establish fMRI as a clinical tool in rehabilitative medicine and allow its use for identifying intervention targets.

Figure 1 below illustrates the randomized, double-blind, sham controlled dosing trial of rTMS for the treatment of aphasia (**AIM 1**).

Figure 1. Diagram of the proposed nerTMS double-blind treatment protocol (**AIMS 1-2**) and associated testing ("AT qualitative and quantitative AT; AT – quantitative testing only).

[figure not shown]

Figure 2 below illustrates the open-label study of combined rTMS and CIAT for the treatment of aphasia (AIM 3).

[figure not shown]

Figure 2. Diagram of the proposed nerTMS+CIAT open-label treatment protocol (AIM 3) and associated testing (Abbreviations as in Figure 1)

DETAILED STUDY PROTOCOL

DAY 1 (enrollment)

Subject identified by study personnel (or referred to our team for possible study participation by clinicians in the area) will undergo screening for study participation:

The inclusion criteria are:

- Age \geq 19 years

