Language task #2 (event-related verb generation task; ER-VGT)

Language task #3 (semantic/tone decision task; SDTD)

Additional language tasks may be obtained dependent on the results of the neuropsychological aphasia testing.

Language task #4 (paired associates verbal learning task; ER-VLT)

Language task #5 (sentence/picture matching task; ER-ASL)

The total duration of the fMRI procedure will be less than 1 hour which is usually very well tolerated by stroke subjects. Upon completion of the fMRI procedure fMRI data will be processed and forwarded to the rTMS laboratory for entry into the stereotactic system for guidance of the rTMS intervention.

NEXT 3 WEEKS INCLUDE EITHER THE SHAM CONTROLLED BLINDED RTMS STUDY (RTC)

OR

NEXT 2 WEEKS INCLUDE THE COMBINED RTMS AND CIAT INTERVENTION (OBS)

DESCRIPTION OF THE PROCEDURES FOR BOTH IS PROVIDED BELOW

RTMS PORTION

Depending on study assignment (**RTC** or **OBS**) subjects will receive nerTMS as per protocol (Figures 1 and 2):

To test the effect of nerTMS on post-stroke language recovery, we will apply an excitatory stimulation protocol termed "theta burst stimulation" (TBS) to the language areas detected by fMRI in the hemisphere affected by stroke.

RTC: We will apply up to 15 TBS treatments made up of 15 sham, 5 TBS + 10 sham, 10 TBS + 5 sham, or 15 TBS treatments, depending on study arm.

OBS: We will apply 10 daily TBS treatments per participant. Four OBS subjects will receive rTMS and CIAT (see below) within approximately one hour of each other, with the treatment sequence permuted so that, on average, the time between nerTMS and CIAT for each subject will be the same.

Using the Brainsight (TM) Neuronavigation System, coil placement will be targeted individually to the left frontal lobe area (Broca's area) as identified by fMRI. The following previously developed protocol will be followed:

1. Single-pulse TMS is performed to establish resting motor threshold (RMT) and active motor threshold (AMT) with a Magstim 200R stimulator connected through a BistimR module to a 70 mm figure-8 coil.
 - a. RMT is defined as the minimum stimulus intensity that produces a motor evoked response (about 50 μ V in 50% of 10 trials) at rest.
 - b. AMT is defined as the minimum stimulus intensity that produced a motor evoked response (about 200 μ V in 50% of trials) during isometric contraction of the tested muscle at about 10% of maximum force.

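### Aim 2 plans only an in-sample association, which cannot support the stated conclusion that fMRI lateralization predicts recovery and becomes a clinical tool

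*Combined protocol and SAP*

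**What the plan says.** The formal statement of Aim 2 (imaging) proposes to examine how lateralization before nerTMS relates to AT outcomes afterwards, and to "determine whether fMRI language lateralization can predict AT performance following nerTMS". Hypothesis 2 is also framed as correlation: "the degree of the post-intervention recovery will correlate with the degree of the left-sided language shift".

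The Innovation section describes fMRI both as a means of locating stimulation targets and "as a way of predicting the possibility of post-stroke recovery". It attaches the phrase point of no return to the second use, labels it AIM 2, and states that "accomplishing this aim will establish fMRI as a clinical tool in rehabilitative medicine". The background section on functional MRI likewise says that mapping can be used to predict the likelihood of recovery after the intervention.

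On sample size, the plan says "Subjects (15/group) will be randomly assigned to 4 treatment groups". Aim 3 adds an open-label study "on aphasia recovery in a group of 20 LMCA stroke patients". Those patients are also scanned and tested, but they receive CIAT as well and are not assigned to validate Aim 2.

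On predictors, the Day 3 section lists three fMRI language tasks and two optional ones: "Additional language tasks may be obtained dependent on the results of the neuropsychological aphasia testing". On outcomes, the Day 2 table lists ten tests. Post-intervention testing takes place within a week of the last treatment and again three months later. No task, test or time point is designated for Aim 2.

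The document is titled as a protocol and SAP, but its only statistical section is the monitoring guideline in section 7 of the DSMB manual, which does not concern Aim 2. There is no prediction model, definition of recovery, cut-off, accuracy measure, success criterion, resampling, hold-out set or external cohort.

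**The concern.** A significant association and a useful prediction for one patient are different findings. The first says that a slope is probably not zero. The second says that knowing a patient's lateralization index brings the forecast of that patient's outcome usefully closer to the truth, in patients who did not supply the fit. Aim 2 promises the second and describes only the first. With no criterion stated, any significant correlation could be reported as accomplishing the aim, and then as establishing a predictive clinical tool.

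Two features of the plan add to this. Several tasks, tests and time points are available and none is designated, so the best-looking pair could be the one reported. The phrase point of no return also suggests a threshold, and none is defined. What is at stake is the credibility of the Aim 2 conclusion. The randomised comparison in Aim 1 is not affected.

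**Working it through.** The documents give no power calculation, significance level or effect size for Aim 2, so there is no figure of theirs to reproduce. What follows is illustration under stated assumptions.

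**Inputs.** From Aim 1: 15 × 4 = 60 randomised, of whom 15 × 3 = 45 receive some active nerTMS (arms a to c). Assumed: two-sided 0.05, approximately normal data, no dropout.

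**1. Smallest significant correlation.** r = t / √(n − 2 + t²), with t the 97.5% point on n − 2 degrees of freedom.
- n = 45: t = 2.017, so r = 2.017 / √(43 + 4.067) = 0.294.
- n = 60: t = 2.002, so r = 2.002 / √(58 + 4.007) = 0.254.

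**2. What that correlation is worth for one patient.** The share of variance explained is r². The reduction in the SD of the prediction error is 1 − √(1 − r²). If this r were the true value, a median-split classifier would be correct with probability 0.5 + arcsin(r)/π.

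| n | r | r² | Error reduction | Median-split accuracy | 95% CI for r (Fisher z) |
|---|---|---|---|---|---|
| 45 | 0.294 | 8.6% | 4.4% | 59.5% | 0.00 to 0.54 |
| 60 | 0.254 | 6.5% | 3.3% | 58.2% | 0.00 to 0.48 |

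Chance accuracy for the median split is 50%.

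**3. Scope for selection without any cut-off.** Three core tasks by ten tests give 30 correlations. If they were independent and all null, the chance of at least one p < 0.05 is 1 − 0.95³⁰ = 79%. Simulation with an assumed correlation of 0.5 among tasks and 0.5 among tests gives 59% (n = 45) and 60% (n = 60). A second time point would add to this.

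**4. If a threshold were taken from the same data.** This is conditional, because no such search is stated. The setting is a single predictor with no true association, searched for the best cut between its 10th and 90th percentiles. The chi-square rows take a binary outcome with 50% recovering; the t-test row takes a continuous outcome. Chance of p < 0.05 at the best cut:

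| Test | n = 45 | n = 60 |
|---|---|---|
| Chi-square, uncorrected | 38% | 41% |
| Chi-square, continuity-corrected | 19% | 22% |
| t-test on a continuous outcome | 36% | 39% |

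The size depends heavily on the test, but every entry is well above 5%.

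**5. A limit on the remedy.** A rule that accepts any fall in leave-one-out error is too weak. Adding one null predictor lowers that error roughly when its chi-square on 1 degree of freedom exceeds 2, which has probability 0.157. Simulation gives about 16%. The size of the gain and its interval therefore have to be reported, not only its direction.

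**The case against.** The strongest reply is that the Innovation section is advocacy and no analyst would carry it out as an instruction, whereas the wording of Aim 2 is measured. That is partly right, and it is why much of the remedy is rewording. But the prediction goal is also in the formal aim, and nothing there says what result would count as prediction.

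A second reply also has force: the clinical-tool sentence covers locating stimulation targets as well as predicting recovery. The criticism therefore applies only to the predictive half of that sentence.

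A third reply is that no threshold analysis is planned. This stands. A reader might infer from the phrase point of no return that the trial will search its own data for a cut-off and declare a chance split predictive. The documents do not say so. The phrase appears once, in parentheses, no dichotomy of outcome is described, and a threshold could be fixed from earlier data. The 19% to 41% range describes what such a search would do, not what the plan does. A reader might also infer that treatment would be withheld from patients beyond the threshold; nothing in the documents proposes that.

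Finally, the gap is part of a wider absence of analysis detail. That is true, but Aim 2 has a specific mismatch between analysis and conclusion that a generic analysis section would not necessarily repair.

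**Conclusion.** The point holds in this form: the association described for Aim 2 does not support the predictive conclusion attached to it. At an assumed two-sided 5% level, a correlation as small as 0.25 to 0.29 would be significant while reducing an individual's prediction error by only 3% to 4%. This does not depend on any cut-off being used. It rests on the assumed significance level, complete data, and an analysis set of 45 or 60, since the documents do not say which patients enter Aim 2.

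The threshold figures are conditional. They show why any point of no return would need protection, not that the plan contains a faulty search. The absence of any check outside the fitted data is established by the documents' silence. It is a matter for correction before Aim 2 is analysed, and it leaves Aim 1 untouched.

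**What to change.** 1. Before any AT outcome is viewed, name one lateralization index (task and region), one AT outcome and one time point for Aim 2, and state which patients are analysed.
2. Keep lateralization continuous. Report how much prediction error falls when it is added to a model with baseline AT, corrected for optimism by cross-validation or bootstrap, with an interval and with every selection step repeated inside the resampling. Do not rest the claim on the direction of the change alone.
3. If a threshold is reported, fix both it and the definition of recovery before any AT outcome is viewed, or reselect the threshold inside the resampling. Give sensitivity and specificity with intervals. Fixing it merely before unblinding is not enough: the blind covers treatment assignment, and the link between lateralization and AT is visible in pooled blinded data.
4. Reword the Innovation section so that the prediction result is reported as an association or as hypothesis-generating, with the predictive clinical-tool and point-of-no-return claims deferred to an independent sample. The target-localization statement need not change on this account.

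The cost is a few paragraphs of analysis text and a modest amount of computing on data already to be collected. No extra patients or visits are needed. The price is a more modest claim for Aim 2.

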- LMCA stroke as indicated by the presence of aphasia and MRI lesion in the LMCA distribution
- Moderate aphasia (Token Test score between 40th and 90th percentile)
- Fluency in English
- Provision of written informed consent by the patient and/or the next of kin

The exclusion criteria include:

- Age less than 19 years
- Underlying degenerative or metabolic disorder or supervening medical illness
- Severe depression or other psychiatric disorder
- Positive pregnancy test in women of childbearing age
- Any contraindication to MRI/fMRI at 3T (i.e., intracranial metal implants, claustrophobia)
- Any contraindication to nerTMS (e.g., seizures or epilepsy)

Screening will also include a complete medical history, details of the precipitating event, physical examinations, complete baseline and ongoing vital sign assessments, neurological evaluations, laboratory results and diagnostic imaging performed. Screening assessments will be performed by the clinician involved in the care of the patient to determine subject eligibility criteria especially neurological examination, which will be documented as part of the patients' medical record.

For the randomized controlled trial (RTC; Figure 1), once informed consent and HIPAA authorization for research are obtained, the subject will be randomized. Randomization will be conducted by the study biostatistician and will be implemented using a standard sealed envelope process.

For the un-blinded observational study (OBS; Figure 2), once informed consent and HIPAA authorization for research are obtained, the subject will be scheduled for group therapy with CIAT where rTMS will be used as a primer for improved rehabilitation outcomes. Three to four subjects will be scheduled concurrently in order to achieve the required minimum of 3 subjects per CIAT therapy group. These subjects will not be randomized or blinded to the treatment.

A member of the research study staff will monitor the subjects for continued compliance with Inclusion and Exclusion Criteria. Those subjects who do not meet the continuation criteria will be terminated from the study.

DAY 2 (pre-nerTMS; days 1 and 2 may be combined)
All subjects (RTC or OBS) will undergo the same procedure

Data Collected for Study Enrollment (after signed consent):

Upon Admission:

Demographics

Medical history (including any chronic underlying disease and medications)

Contact information to include phone number

Time, date, and mechanism of stroke

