Neurological Examination (see below)

Neuropsychological testing of aphasia will include:

Procedures	NAT 1	NAT 2	NAT 3	NAT 4	NA T 5
Test Version	A	B	A	B	A
Boston Naming Test	X	X	X	X	X
Semantic Fluency Test (letter & category)	X	X	X	X	X
Controlled Oral Word Association Test (COWAT)	X	X	X	X	X
BDAE Complex Ideation subtest	X	X	X	X	X
Peabody Picture Vocabulary Test III (PPVT III)	X	X	X	X	X
Cognitive-Linguistic Quick Test (CLQT) part of neuro exam	X				X
Token Test	X			X	X
WAB-R (AQ) (picture description-verbal discourse sample— see below)	X			X	X
Apraxia Subtest	X			X	X
BDAE Picture Description (written discourse sample) — see below)	X			X	X

Verbal Discourse Prompt (WAB-R)

Take a few minutes to look at this picture. When you are done, I want you to tell me a story about what you see happening. (Set timer to 2 minutes).

If participant states he/she is ready before two minutes provide the following cue: *You have a little more time to look at the picture to help you tell a story. Use this time to help develop your story.*

When the two minutes is up, say, *"Tell me your story."*

Written Discourse Prompt (BDAE)

Take a few minutes to look at this picture. *When you are done, I want you to write me a story about what you see happening. (Set timer to 2minutes).*

If participant states he/she is ready before two minutes provide the following cue: *You have a little more time to look at the picture to help you write a story. Use this time to help develop your story.*

When the two minutes is up, say, *"Write your story."*

Discourse samples will be elicited by the tester prior to, immediately after, and 3 months after intervention (nerTMS). These tests will be administered as part of the aphasia testing. Testing procedures will be audio and/or video recorded.

DAY 3 (may be combined with previous procedures)
All subjects (RTC or OBS) will undergo the same procedure

Functional MRI

FMRI Scanning Procedures have been refined over the course of our experiences with numerous healthy and stroke subjects undergoing studies of language [3, 4, 12-14, 85-93]. These procedures provide high success rate in the completion of fMRI experiments. All subjects will undergo standard radiology screening for MRI compatibility at 3T. The subjects will be carefully oriented to the equipment and will engage in explicit practice of all of the tasks' requirements. We will utilize the following *fMRI language paradigms*:

Language task #1 (block design verb generation task; BD-VGT)

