All procedures will be performed within 1 week of the last rTMS/CIAT intervention and then 3 months later following the above described protocols.

Upon completion of the above procedures subjects will be dismissed from the study. Further follow up will be provided by primary neurologist or primary care provider.

NEUROLOGICAL EXAMINATION

Standard neurological examination will be performed by [name] or his designee at the initiation of the study (after the patient signs the consent form) and after completion of the study (around the time of final neuropsychological testing of aphasia ~3 months after completion of the intervention). This examination will include:

	Study enrollment	Study termination	Change*
Date of exam			
Vital Signs			
Blood Pressure			
Heart Rate			
Finger stick blood glucose			
Cranial nerve examination			
Visual fields			
Ophtalmoscopic examination			
Pupils			
Eye movements (CN 3,4,6)			
Facial symmetry			
Auditory assessment			
Palate			
Shrug			
Tongue examination (midline)			
Muscle strength right upper extremity (MRC)			
Muscle strength left upper extremity (MRC)			
Muscle strength right lower extremity (MRC)			
Muscle strength left lower extremity (MRC)			
Muscle stretch reflexes right upper extremity			
Muscle stretch reflexes left upper extremity			
Muscle stretch reflexes right lower extremity			
Muscle stretch reflexes left lower extremity			
Coordination right upper extremity			
Coordination left upper extremity			
Gait			
Mechanism of ischemic stroke**			

* (-1 = worse after intervention; 1 = improved after intervention; 0 = no change)

** (small vessel = 1; large vessel = 2; embolic = 3 ; hypercoagulable state = 4; unknown = 5)

Participants requiring additional protections

Regarding cognitively impaired subjects: All subjects will be enrolled in the study based on voluntary basis. The patients will not be approached until the purposed of the study is explained to the patient by the physician directly involved in the care of the patient and a verbal permission is obtained from the patient (and family member/significant other if appropriate) regarding the contact with the study personnel. After screen is complete and the subject is found to be eligible, she/he will receive the consent form for review. After at least 24 hours the patient will be contacted regarding the study. If interested and have correctly answered all questions on both the Consent Form

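### One fixed form order (A-B-A-B-A) for every subject means that, for tests with two forms, form difficulty cannot be separated from visit; within-arm and externally controlled readings are exposed, randomised contrasts are not

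*Combined protocol and SAP*

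**What the plan says.** The neuropsychological testing table in the Detailed Study Protocol, DAY 2, has one row for form: "Test Version A B A B A". The DAY 2 heading states "All subjects (RTC or OBS) will undergo the same procedure". No second sequence is given. Counterbalancing, equating of forms and a form term in an analysis are not mentioned anywhere.

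Some tests are marked at all five visits, for example "Boston Naming Test X X X X X". Others, such as "Token Test X X X", are marked at three; in the table these marks stand under NAT 1, NAT 4 and NAT 5. The two discourse samples fall on the same three visits, and the text below the table fixes their timing: "Discourse samples will be elicited by the tester prior to, immediately after, and 3 months after intervention (nerTMS". Post-Intervention Procedures agrees: "All procedures will be performed within 1 week of the last rTMS/CIAT intervention and then 3 months later following the above described protocols".

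The uses of these scores are stated broadly. Aim 1 says "Short- and long-term outcomes will be evaluated with aphasia testing (AT) and fMRI". Aim 3 says "Patients will be evaluated with fMRI and AT as above and compared to the arm", and goes on to name arm b of the randomised study and CIAT data from a separate ongoing study.

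**The concern.** When two forms of a test differ in difficulty, the difference enters any change score that crosses forms. Here the short-term change crosses forms and the long-term change does not, so the two are not measured alike within an arm. If form B is easier, an arm with no true change appears to gain by the end of treatment and to lose the gain by 3 months. If form B is harder, a real early gain is hidden and then looks like late recovery.

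The OBS group has no randomised control. Nothing in the design therefore guarantees that a form effect cancels in its own pre-post change, or in its comparison with data from another study.

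**Working it through.** The plan gives no alpha, SD, effect size or sample-size derivation, so there is no figure of its own to reproduce.

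**1. Form at each time point.** The discourse rows (NAT 1, 4, 5), set beside the text on their timing, give NAT 1 = baseline, NAT 4 = immediately after treatment and NAT 5 = 3 months. The form row makes these A, B and A.

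**2. Effect on change.** Let δ be the mean score on form B minus that on form A.

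- NAT 1 to NAT 4 (A to B): true change + δ
- NAT 1 to NAT 5 (A to A): true change + 0
- NAT 4 to NAT 5 (B to A): true change − δ
- Active minus sham, NAT 1 to NAT 4: (change in active + δ) − (change in sham + δ), so δ drops out

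**3. Can analysis remove δ?** Take a model with four arms, five categorical visits, their interaction and a form term: 1 + 4 + 3 + 12 + 1 = 21 columns. Under the fixed order the form B indicator equals the sum of the NAT 2 and NAT 4 indicators, so the rank is 20 and form is not estimable. With half the subjects on A-B-A-B-A and half on B-A-B-A-B, the rank is 21 and form is estimable. Forcing time to be linear also makes form estimable under the fixed order (9 columns, rank 9), but only through that assumption.

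**4. Illustrative size.** Inputs from the documents: 15 per arm (Aim 1) and 20 in OBS (Aim 3). Assumptions not in the documents: form difference d of 0.1, 0.2 or 0.3 SD, test-retest correlation r = 0.8, no true change, and a paired t test at two-sided 5%.

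SD of change = √(2(1 − r)) = √0.4 = 0.632. Noncentrality = (d / 0.632) × √n. For d = 0.3 and n = 15: (0.3 / 0.632) × 3.873 = 1.84. The noncentral t distribution on n − 1 degrees of freedom gives the chance of a false change:

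| d (SD) | n = 15 | n = 20 |
|---|---|---|
| 0 | 5% (nominal) | 5% (nominal) |
| 0.1 | 9% | 10% |
| 0.2 | 21% | 27% |
| 0.3 | 40% | 52% |

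At d = 0.3 the range over the correlation is 29% (r = 0.7) to 68% (r = 0.9) for n = 15, and 38% to 81% for n = 20.

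**5. Randomised contrast.** A simulation of 15 v 15 with r = 0.8, and the same form shift of 0.2 or 0.5 SD in both arms, gave type I error of 4.9% to 5.0% and no mean bias. This agrees with step 2.

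**The case against.** The strongest reply is that the main question is untouched. Hypothesis 1 is framed against sham, every arm gets the same form at the same NAT, and long-term benefit can be tested against arm d at NAT 5 in the same way. Arm d would also reveal a shared form effect, because sham subjects would appear to gain and then lose. All of this stands. A shift common to all subjects would also leave the correlation of individual recovery with fMRI shift (Hypothesis 2) unchanged. Alternating forms is, besides, a recognisable way to limit practice on repeated items.

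Four stronger readings are tempting, and the documents do not support them:

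- A reader might infer that the plan specifies a within-arm durability test or a single-arm OBS test. It states neither. Aim 1 mentions short- and long-term outcomes inside a sham-controlled aim, and Aim 3 names only arm b and the external CIAT data. The false-change rates above are conditional on such a test being used.
- A reader might infer that the 2-week OBS group ends at NAT 3 (form A) while arm b ends at NAT 4 (form B). Figure 2 is not shown in the text available for this review, and the table points the other way: discourse samples are required immediately after intervention and are marked at NAT 4, not NAT 3, and one procedure covers both groups.
- A reader might infer that in arm c the sham weeks are A to A and the active week A to B. The text does not give the timing of NAT 2 and NAT 3, Figure 1 is not shown, and no such within-subject comparison is stated.
- A reader might infer that every test, including the Token Test and WAB-R, has two forms. The documents do not say which do, and they give one prompt per discourse task. A test with one form has no form effect.

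What remains is that the sponsor cannot tell form from visit in any reading that is not a same-visit contrast between randomised arms.

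**Conclusion.** The concern holds in limited form and is minor. For any test that has two forms, the fixed order makes form inseparable from visit. Three readings are exposed: short- versus long-term change within an arm, pre-post change in OBS, and OBS against the external CIAT data if that study used a different form order, which the documents do not give. OBS against arm b is exposed only if the two end at different NATs, and the table suggests that they do not. The randomised comparison with arm d at the same NAT is unbiased.

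The true size is unknown. The 9% to 40% (n = 15) and 10% to 52% (n = 20) are illustrations that rest on assumed form differences, an assumed correlation of 0.8 and a paired test that the plan does not state. If the forms are equal, there is no bias. The placing of NAT 4 as post-treatment is firm for the randomised study and probable for OBS.

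**What to change.** State which tests have two forms. For those tests, assign about half of each randomised arm (8/7) and half of OBS (10/10) to A-B-A-B-A and the rest to B-A-B-A-B, set at allocation or enrolment, and include form in the model for the aphasia tests. Baseline to 3 months then stays on one form for each subject, and δ enters baseline to post-treatment change with opposite signs in the two halves. With an 8/7 split the unadjusted remainder is δ × (8 − 7)/15 = δ/15, which the model term removes.

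The cost is one more item on the allocation list, one model degree of freedom and a very small loss of precision. If one arm is split 8/7 and the other 7/8, the correlation of arm with order is (8×8 − 7×7)/(15×15) = 0.067, and the variance of the arm contrast rises by a factor of 1/(1 − 0.067²) = 1.0045, or under 0.5%. No visits, tests or subjects are added.

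For subjects already tested, base NAT 4 and NAT 5 conclusions on contrasts with arm d at the same NAT, and do not use within-arm NAT 4 versus NAT 5 change as evidence of durability. For Aim 3, report the form order in OBS and in the external CIAT study beside the comparison.
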